### **5.3.3 Activity**

There are no restrictions on activity during the study.

## **5.4 Screen failures**

Screen failures are defined as participants who consent to participate in the clinical study but are not subsequently randomized to study treatment. A minimal set of screen failure information is required to ensure transparent reporting of screen failure participants to meet the Consolidated Standards of Reporting Trials publishing requirements and to respond to queries from regulatory authorities. Minimal information includes demography, screen failure details, eligibility criteria, and any serious adverse event (SAE).

Individuals who do not meet the criteria for participation in this study (screen failure) may be rescreened, following discussion with the sponsor's medical monitor or study physician. Rescreened participants should be assigned a new participant number for rescreening and repeat all Visit 1 assessments.

If a study participant has 1 isolated test result outside the specific range which is deemed clinically nonsignificant, the abnormal value may be rechecked at the discretion of the investigator, following discussion with the sponsor's medical monitor or study physician. If the normalization of the test result occurs within the Screening Period, then no other Screening procedures need to be repeated and the study participant may be randomized, provided all other eligibility criteria are met.

Tests that result in ALT, AST, or ALP up to 25% above the exclusion limit at Screening may be repeated once for confirmation. Eligibility assessment will be based on the best of the 2 results available before initiating randomized treatment.

## **6 STUDY TREATMENTS**

Study treatment is defined as any investigational treatment(s), marketed product(s), placebo, or medical device(s) intended to be administered to a study participant according to the study protocol.

### **6.1 Treatments administered**

Eligible study participants will be randomized 1:1 to receive rozanolixizumab [REDACTED] or placebo (0.9% saline) by sc infusion [REDACTED] for 24 weeks. The interval between administration of 2 consecutive doses should be [REDACTED] days. A summary of the treatment administered is provided in Table 6-1.

**Table 6-1: Study medications administered**

Study treatment name	Rozanolixizumab	Placebo
Dose formulation	Solution for injection	Solution for injection
Unit dose strength(s)	A vial of rozanolixizumab at a concentration of 140mg/mL, formulated with [REDACTED] [REDACTED]	0.9% sodium chloride aqueous solution (physiological saline, preservative free)
Dosage level(s)	[REDACTED]	Not applicable
Route of administration	Subcutaneous infusion	Subcutaneous infusion
Post-dose observation	On dosing days, for the first 2 weeks (Visit 2 and Visit 5), a 4-hour post-dose observation will be in place. Assuming the first 2 doses were well tolerated, on dosing days in Week 3, 4, and 5 (Visit 6, Visit 7, and Visit 8), a 1-hour post dose observation will be in place. Assuming the first 5 doses were well tolerated, on subsequent weeks, a 15-minute post-dose observation will be in place. Following a missed dose due to temporary IMP discontinuation, a 1-hour observation will be in place for the first 2 doses followed by a 15-minute observation per above. The minimum post-dose observation time frame may be extended at the discretion of the investigator or study nurse at home dosing visits. These recommendations are applicable for dosing at site and at home except where specified. The investigator is required to complete a check list to confirm that all conditions for home dosing have been met (as outlined in Section 8) prior to the start of home dosing.	
Use	Experimental	Placebo comparator
Sourcing	Provided centrally by the sponsor	Provided centrally by the sponsor
Packaging and labeling	Packaging will be described in the IMP Handling Manual. Packaging will be 47abelled as required per country requirement.	Packaging will be described in the IMP Handling Manual. Packaging will be 47abelled as required per country requirement.
Current/Former name(s) or alias(es)	UCB7665	Not applicable

IMP=investigational medicinal product; w/v=weight/volume

## 6.2 Preparation, handling, storage, and accountability requirements

The investigator or designee must confirm appropriate temperature conditions have been maintained during transit for all study treatment received and any discrepancies are reported and resolved before use of the study treatment.

Only participants enrolled in the study may receive study treatment and only authorized site staff or healthcare professionals may supply or administer study treatment. All study treatments must be stored in a secure, environmentally controlled, and monitored (manual or automated) area in

accordance with the labeled storage conditions with access limited to the investigator and authorized site staff.

Details on the preparation of study treatment for infusion, rate of infusion, administration, appropriate records handling, and blinded and unblinded site personnel roles are provided in the IMP Handling Manual. All site personnel and healthcare professionals delegated to handle study treatment storage, preparation, and administration must be trained to IMP Handling Manual.

The investigator or delegate is responsible for study treatment accountability, reconciliation, and record maintenance (ie, receipt, reconciliation, and final disposition records).

In case an out-of-range temperature is noted, it must be immediately reported as per instructions contained in the IMP Handling Manual.

Further guidance and information for the final disposition of unused study treatment are provided in the IMP Handling Manual.

### **6.2.1 Drug accountability**

A Drug Accountability form will be used to record study medication dispensing and return information on a by-participant basis and will serve as source documentation during the course of the study. Details of any study medication lost, damaged (due to breakage or wastage), not used, partially used, disposed of at the study site, or returned to the sponsor or designee must also be recorded on the appropriate forms. All supplies and pharmacy documentation must be made available throughout the study for UCB (or designee) to review.

The investigator may assign some of the investigator's duties for drug accountability at the study site to an appropriate pharmacist/designee and/or the healthcare professional.

The investigator (or designee) is responsible for retaining all used, unused, and partially used containers of study medication until returned or destroyed.

The investigator must ensure that the study medication is used only in accordance with the protocol.

Periodically, and/or after completion of the clinical phase of the study, all used (including empty containers)/partially used, unused, damaged, and/or expired study medication must be reconciled and either destroyed at the site according to local laws, regulations, and UCB Standard Operating Procedures or returned to UCB (or designee). Investigational medicinal product intended for the study cannot be used for any other purpose than that described in this protocol.

### **6.3 Measures to minimize bias: randomization and blinding**

An interactive response technology (IRT) will be used for assigning eligible study participants to a treatment regimen (as applicable) based on a predetermined production randomization and/or packaging schedule provided by UCB (or designee). The randomization schedule will be produced by the IRT vendor. The IRT will generate individual assignments for kits of study medication, as appropriate, according to the visit schedule.

To enroll a study participant (Visit 1), the investigator or designee will contact the IRT and provide brief details about the participant to be enrolled. Each study participant will receive a 5-digit number assigned at Screening that serves as the study participant identifier throughout the study. The study participant number will be required in all communication between the

investigator or designee and the IRT regarding a particular study participant. Study participant numbers and kit numbers will be tracked via the IRT.

To randomize a study participant, the investigator or designee will contact the IRT and provide brief details about the study participant to be randomized. The IRT will automatically inform the investigator or designee of the study participant's randomization number. The IRT will allocate kit numbers to the study participant based on the participant number during the course of the study. The randomization number must be incorporated into the eCRF.

The randomization will be stratified by:

- Time from disease symptom onset ( $\leq$ 6 months or  $>$ 6 months from disease symptom onset)
- Cognitive function (RBANS score of  $\leq$ 85 or  $>$ 85)

Early initiation of therapy ( $<$ 6 months from symptom onset) and detection of a plasma membrane protein antibody were independent predictors of favorable seizure outcome ( $p$  $<$ 0.01; Dubey et al, 2017).

### **6.3.1 Procedures for maintaining and breaking the treatment blind**

#### **6.3.1.1 Maintenance of study treatment blind**

All study participant treatment details will be allocated and maintained by the IRT system.

The following individuals will receive the randomization code at the start of the study:

- Designated bioanalytical staff analyzing PK samples
- IRT provider

The IMP for rozanolixizumab and placebo will not be identical in appearance. Therefore, study site pharmacists, other suitably qualified site personnel, or healthcare professionals who are responsible for preparation of IMP treatments will have access to treatment allocations for individual study participants via the IRT. The unblinded pharmacy monitors from the Contract Research Organization (CRO) and the Clinical Supply Set-Up Manager/Clinical Supply Planner, and the unblinded Clinical Project Manager (or designee) will also have access to the treatment allocations and to the drug accountability records, if applicable. Further details are provided in the IMP Handling Manual and Site Unblinded Team Management Plan.

Due to differences in presentation between rozanolixizumab and placebo, special precautions will be taken to ensure blinding. Both products have packaging differences (unblinded labels) but also physical appearance differences (volumes, color, viscosity). The IMP preparation will be performed by unblinded personnel (unblinded qualified site staff or unblinded home healthcare practitioner at the participant's home). Please note that the difference in appearance of the two IMPs can be seen in the syringe but not in the tubing. Therefore, only the syringe will be covered by blinding stickers (see IMP Handling Manual).

The IMP administration will be performed by blinded personnel (blinded qualified site staff or blinded home healthcare practitioner at the study participant's home).

The following individuals may, as necessary, have access to the randomization code as indicated:

- Sponsor Patient Safety staff as needed for reporting SAEs to regulatory authorities.

- Members of the IDMC who participate in unblinded sessions will be given information about the IMP allocation for those study participants for whom data are provided at these sessions.
- The designated unblinded statistician and supporting programmer(s) responsible for the preparation of the data outputs for the IDMC review and/or any interim analyses.

Certain clinical laboratory results have the potential to unblind the investigator, site personnel, and study team. These results will not be reported to investigative sites or other blinded personnel (see Section 10.2 for a list of these clinical laboratory parameters). A medical monitor independent from the sponsor and unblinded to the serum IgG and albumin levels, but blinded to actual treatment assignment (an independent unblinded medical monitor) will monitor these parameters during the Treatment Period. If temporary treatment discontinuation due to low serum IgG levels or low serum albumin levels (as per Section 7.1.4) is required, the independent unblinded medical monitor will contact the IRT system to initiate mock infusions with only placebo. This procedure will take place irrespective of the randomized IMP. Allocation of mock kit numbers will be handled via the IRT. The independent unblinded medical monitor will re-initiate the IMP via the IRT system when the serum IgG and/or albumin levels have returned to protocol defined thresholds specified in Section 7.1.4.

Further details of maintenance of the study treatment blind are provided in the IMP Handling Manual and Site Unblinded Team Management Plan.

#### **6.3.1.2      Breaking the treatment blind in an emergency situation**

In the event of an emergency, it will be possible to determine to which treatment arm the participant has been allocated by contacting the IRT. All sites will be provided with details of how to contact the system for code breaking at the start of the study. The medical monitor or equivalent should be consulted prior to unblinding, whenever possible.

The clinical project manager and medical monitor will be informed immediately via the IRT when a code is broken but will remain blinded to specific treatment information. Any unblinding of the study medication performed by the investigator must be recorded in the source documents and on the Study Termination eCRF page.

Inadvertent unblinding has to be listed as a major protocol deviation.

### **6.4           Treatment compliance**

Drug accountability must be recorded on the Drug Accountability form (Section 6.2.1).

### **6.5           Concomitant medication(s)/treatment(s)**

#### **6.5.1        Permitted concomitant treatments (medications and therapies)**

Investigator should take utmost precaution for the dosage of concomitant medications for study participants who might have impaired renal function (GFR 30ml/min/1.73m^2 to 45ml/min/1.73m^2) and should refer to the prescribing information for potential dose adjustment.

Given that study participants will be administered steroids up to Week 12 of the study, it is up to the discretion of investigator to initiate prophylaxis for pneumocystis carinii pneumonia if deemed appropriate.

The following concomitant medications are permitted during the study:

- Antiepileptic drugs: all study participants should preferably continue to take their Baseline AED regimen unchanged over the whole study period. Decreases in daily dose or discontinuation of AEDs are permitted, per investigator assessment. However, initiation of new AEDs or dose increase of a AED are not allowed.
- Corticosteroids (only as specified in the protocol)
- Topical steroids: the use of topical or local is permitted
- Antipsychotics: the dose should be stable within 1 week of the cognitive assessments
- Benzodiazepines may be used if at stable daily dosage regimen as concomitant medication. However, per needed benzodiazepine treatment that is deemed medically necessary in the opinion of the investigator should be administered, and the study participant's continuation in the study must be discussed between the medical monitor and the investigator.

Administration of COVID-19 vaccines will be recorded in the concomitant medication eCRF page. The specific name of the vaccine and the exact date of administration should be recorded, as instructed in the completion guideline. See Section 8.3.9 for details.

#### **6.5.2 Prohibited prior and concomitant treatments (medications and therapies)**

The following concomitant medications are prohibited during the Treatment Period except for use as specified or as rescue medication:

- High dose corticosteroids (500 to 1000mg MP equivalent/day) within 1 year prior to randomization, for any indication, is prohibited, except:
  - as permitted per protocol inclusion criteria (see Section 5.1)
  - if used as first line AIE treatment in the 6 months prior to randomization (counted from the onset of treatment to randomization date) (see Section 4.1)
- Prednisolone is prohibited during the Treatment Period if used outside of the protocol-specified steroid taper.

All treatments listed in Table 6-2 are prohibited during the Treatment Period, except for use as a rescue medication.

**Table 6-2: Prohibited concomitant treatments and treatment-free period for exclusionary immunosuppressants, biologics, and other therapies prior to Baseline Visit**

Generic name (commercial/trade names)	Timeframe for prohibition
Intravenous or sc Ig	Used within 4 weeks prior to the Baseline Visit
PEX or plasmapheresis	
Immunoabsorption	
Immunosuppressants:	
Cyclophosphamide	Any use prior to the Baseline Visit
Pimecrolimus	Used within 4 weeks prior to the Baseline Visit
Vinca alkaloids (vincristine, vinblastine)	Used within 12 weeks prior to the Baseline Visit
Azathioprine	
Mycophenolate mofetil	
Biologics (mAbs and fusion proteins):	
Eculizumab	Used within 3 months prior to the Baseline Visit
Abatacept (CTLA 4-Ig)	Used within 6 months prior to the Baseline Visit
Belimumab	
Golimumab	
Natalizumab	
Ofatumumab	
Veltuzumab	
Satralizumab	
Other biologics	
Rituximab	Used within 6 months prior to the Baseline Visit, or used $\geq$ 6 months prior to the Baseline Visit with B cells that have not returned to normal levels
Ocrelizumab	
Inebulizumab	
TACI-Ig (Atacicept)	Used within 10 months prior to the Baseline Visit

**Table 6-2: Prohibited concomitant treatments and treatment-free period for exclusionary immunosuppressants, biologics, and other therapies prior to Baseline Visit**

Generic name (commercial/trade names)	Timeframe for prohibition
Others	
Antineoplastic or treatments for neoplastic disease (including Anti-PD-1 mAb)	Used within 3 months prior to the Baseline Visit

Anti-PD-1=anti-program cell death-1; CTLA-4=cytotoxic T-lymphocyte-associated protein 4; Ig=immunoglobulin; mAb=monoclonal antibody; PEX=plasma exchange; sc=subcutaneous

### **6.5.3      Rescue medication**

Rescue medication considered most appropriate for the study participant will be selected by the investigator. The study site will supply rescue medication that will be obtained locally. The effect of rozanolixizumab on the efficacy of IgG biologics and Fc-fusion proteins is not known.

Although the use of rescue medication is allowable at any time during the study, the use of rescue medications should be delayed, if clinically feasible, for at least 4 weeks following the initiation of study treatment. Study participants who require rescue medication will discontinue blinded treatment, and complete the assessments for the Edisc Visit. Following this, the selection of an appropriate rescue medication will be made at the investigator's discretion, and the study participant will enter the SFU Period during which unscheduled visit' may be performed. Rescue medications are permitted during the SFU Period.

### **6.6      Dose modification**

Dose modifications of IMP are not permitted in this study.

### **6.7      Criteria for study hold or dosing stoppage**

The sponsor's decision for study hold or dosing stoppage will be based on IDMC recommendation.

### **6.8      Treatment after the end of the study**

Study participants who complete the 24-week Treatment Period and require further treatment may have the option to access rozanolixizumab via another clinical study or an access program, if available, as per local laws and regulations. The participant should discuss any alternative treatment options (if needed after the study) with their healthcare provider.

## **7      DISCONTINUATION OF STUDY MEDICATION AND PARTICIPANT DISCONTINUATION/WITHDRAWAL**

[figure not shown]
### **7.1      Discontinuation of study medication**

Participants who are permanently discontinued from IMP will undergo an EDisc and SFU Visit. In addition to algorithmic stopping criteria, management of AEs is ultimately at the investigator's discretion.

### 7.1.1 Liver chemistry stopping criteria

Discontinuation of study treatment for abnormal liver function should be considered by the investigator when a participant meets one of the conditions outlined [Figure 7-1](#) or if the investigator believes that it is in best interest of the participant.

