### **Diagnostic assessments**

24b Alanine transaminase (ALT), aspartate aminotransferase (AST), or alkaline phosphatase (ALP) are  $>3$ x upper limit of normal (ULN).

- If study participant has  $>$ ULN for ALT, AST, or ALP that does not meet the exclusion limit at Screening, the tests must be repeated prior to dosing to ensure there was no further ongoing clinically relevant increase. In case of a clinically relevant increase as per the investigator's judgement, the study participant must be excluded.
- Tests that result in ALT, AST, or ALP up to 25% above the exclusion limit ( $>2$ xULN) may be repeated once for confirmation. This includes rescreening. If any of the repeated tests (ALT, AST, or ALP) are  $>2$ xULN, the study participant will meet the exclusion criterion #24b and the study participant must be excluded.
- For randomized study participants with a Baseline result  $>$ ULN for ALT, AST, ALP, or total bilirubin but  $<1.5$ xULN, a Baseline diagnosis and/or the cause of any clinically meaningful elevation will have to be understood and recorded in the electronic case report form (eCRF).

25. Bilirubin  $>1.5$ xULN (isolated bilirubin  $>1.5$ xULN is acceptable if bilirubin is fractionated and direct bilirubin  $<35\%$ ).

26. Removed in Protocol Amendment 5 as already incorporated in exclusion criterion #10.

27. Removed in Protocol Amendment 2, and incorporated in exclusion criterion #24.

28. Removed in Protocol Amendment 2, and incorporated in exclusion criterion #24.

29. Removed in Protocol Amendment 2, and incorporated in exclusion criterion #24.

30a. Study participant has a total IgG level  $\leq 5.5$ g/L at the Screening Visit.

31. Study participant has absolute neutrophil count  $<1500$  cells/mm^3 at the Screening Visit.

32. Study participant has a planned major elective surgical procedure for the duration of their participation in the study.

33. Removed in Protocol Amendment 4.

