**Figure 7-1: Liver Chemistry Stopping Criteria and Increased Monitoring Algorithm**

AST= aspartate aminotransferase; ALT=alanine transaminase; INR=international normalized ratio; SAE=serious adverse event; ULN=upper limit of normal

Specific assessments and follow-up actions for potential drug-induced liver injury are provided in Appendix 6 (Section [10.6](#)).

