### 7.1.2 Permanent discontinuation due to other AEs

Study participants **must be permanently discontinued from IMP** if any of the following safety-related events occur:

1. Study participant develops an illness that would interfere with his/her continued participation.
2. Study participant has a significant infective episode including but not limited to bacteremia/sepsis, infectious meningitis, septic arthritis, osteomyelitis, complicated pneumonia, or visceral abscess which may or may not result in hospitalization. This list is not intended to be all inclusive, and the investigator is expected to apply their judgement on continuing IMP based on the clinical situation (see Appendix 14; Section [10.14](#)).

---

3. Study participant has an AE of severe or serious hypersensitivity infusion-related reaction (see Appendix 15; Section 10.15) or anaphylaxis requiring corticosteroid and/or epinephrine therapy (Sampson et al, 2006).
4. Study participant has a recurrence of aseptic meningitis (Section 10.13).
5. Study participant who develops active TB, LTBI, or NTM infection during the study, regardless of initiation of TB treatment.
6. Study participant has active suicidal ideation as indicated by a positive response (Yes) to either Question 4 or Question 5 of the “Since Last Visit” version of the C-SSRS. The study participant should be referred immediately to a mental healthcare professional.
7. Study participant has new onset or recurrent neoplastic disease (except for superficial basal or squamous cell carcinoma of the skin not requiring targeted biological therapy, chemotherapy or radiation).

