**Protocol-Required Safety Laboratory Assessments**

Laboratory Assessments	Parameters			
	Creatinine	Sodium	Alanine aminotransferase (ALT)/ serum glutamic-pyruvic transaminase (SGPT)	Total protein b Albumin b
	Glucose (non-fasting)	Calcium	Alkaline phosphatase	
	Lactate dehydrogenase (LDH)	C-reactive protein (CRP)	Low-density lipoprotein (LDL) High-density lipoprotein (HDL) Total cholesterol Triglycerides	
Routine Urinalysis	
 
Specific gravity
 
pH, glucose, protein, blood, ketones, bilirubin, urobilinogen, nitrite, leukocyte esterase by dipstick
 
Microscopic examination (if blood or protein is abnormal)
 
			
Other Screening Tests	
 
Follicle-stimulating hormone (FSH) and estradiol (as needed in women of non-childbearing potential only)
 
Serum or urine alcohol and drug screen (to include at minimum: amphetamines, barbiturates, cocaine, opiates, cannabinoids and benzodiazepines)
 
Serum human chorionic gonadotropin pregnancy test (as needed for women of childbearing potential)
 
Serology testing (for Hepatitis A, Hepatitis B surface antigen, Hepatitis C virus antibody, and human immunodeficiency virus [HIV])
 
			
Other Tests	
The following tests are performed locally:
 
 
IGRA TB test
 
Dipstick urinalysis (including any microscopy where required)
 
Urine pregnancy dipstick testc
 
			

IGRA=interferon-gamma release assay; TB=tuberculosis.

The results of each test must be entered into the CRF.

NOTES:

a Details of liver chemistry stopping criteria and required actions and follow-up assessments after liver stopping or monitoring event are given in Section 10.6 (Appendix 6). All events of ALT  $\geq 3 \times$  upper limit of normal (ULN) and bilirubin  $\geq 2 \times$  ULN ( $>35\%$  direct bilirubin) or ALT  $\geq 3 \times$  ULN and international normalized ratio (INR)  $>1.5$ , if INR measured, may indicate severe liver injury (possible Hy's Law) and must be reported as an SAE (excluding studies of hepatic impairment or cirrhosis).

b The results of these assessments will not be reported to investigative sites or other blinded personnel until the study has been unblinded, unless a safety alert requires a clinical review of the study participant.

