## 10.6 Appendix 6: Liver Safety – Suggested Actions and Follow-up Assessments

Participants with potential drug-induced liver injury must be assessed to determine if study medication must be discontinued. In addition, all concomitant medications and herbal supplements that are not medically necessary should also be discontinued.

Investigators should attempt to obtain information on study participants in the case of study medication discontinuation to complete the final evaluation.

Study participants with potential drug-induced liver injury should not be withdrawn from the study until investigation and monitoring are complete. All results of these evaluations and observations, as well as the reason(s) for study medication discontinuation and/or participant withdrawal (if applicable), must be recorded in the source documents. The eCRF must document the primary reason for discontinuation of study medication.

A specific monitoring plan must be agreed between the study physician and the investigator for study participants who have ALT >3 ULN. The monitoring plan should include any necessary follow-up assessments (until resolution of the abnormal lab values). Liver chemistry stopping criteria and criteria for increased monitoring are designed to assure study participant safety and to evaluate liver event etiology. They are presented in the tables below.

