### Phase 2 Liver Chemistry Stopping Criteria and Follow-Up Assessments

Liver Chemistry Stopping Criteria	
ALT-absolute	ALT $\geq$ 5xULN
ALT Increase	ALT $\geq$ 3xULN persists for $\geq$ 4 weeks
Bilirubina,b	ALT $\geq$ 3xULN and bilirubin $\geq$ 2xULN ( $>35\%$ direct bilirubin)
INRb	ALT $\geq$ 3xULN and international normalized ratio (INR) $>1.5$ , if INR measured
Cannot Monitor	ALT $\geq$ 3xULN and cannot be monitored weekly for 4 weeks
Symptomaticc	ALT $\geq$ 3xULN associated with symptoms (new or worsening) believed to be related to liver injury or hypersensitivity
Suggested Actions and Follow-up Assessments	
Actions	

• Immediately discontinue study medication.

• Report the event to UCB within 24 hours.

	
Follow-Up Assessments	

• Viral hepatitis serologyd

	

Liver Chemistry Stopping Criteria	

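### The protocol gives the liver stopping criteria inconsistent force: Section 7.1.1 asks the investigator to consider stopping, Appendix 6 orders a permanent stop under a heading that calls it suggested, and Appendix 2 calls the same actions required

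*Protocol*

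**What the plan says.** Section 7.1.1 applies when a participant meets a condition in Figure 7-1, or when the investigator thinks stopping is in the participant's best interest. For both cases it says: "Discontinuation of study treatment for abnormal liver function should be considered by the investigator". The note under the figure adds: "Specific assessments and follow-up actions for potential drug-induced liver injury are provided in Appendix 6".

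Appendix 6 opens with "Participants with potential drug-induced liver injury must be assessed to determine if study medication must be discontinued". It then lists six stopping criteria:

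- ALT at least 5×ULN
- ALT at least 3×ULN persisting for 4 weeks or more
- ALT at least 3×ULN with bilirubin at least 2×ULN (more than 35% direct)
- ALT at least 3×ULN with INR above 1.5, if measured
- ALT at least 3×ULN that cannot be monitored weekly for 4 weeks
- ALT at least 3×ULN with symptoms of liver injury or hypersensitivity

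The actions that follow tell the site to stop medication immediately, not to restart or rechallenge, and to discontinue permanently. They stand under the heading "Suggested Actions and Follow-up Assessments". Note a to the safety laboratory table in Appendix 2 describes the same material differently: "Details of liver chemistry stopping criteria and required actions and follow-up assessments after liver stopping or monitoring event are given in Section 10.6".

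Two general provisions bear on this. Section 7.1 says "In addition to algorithmic stopping criteria, management of AEs is ultimately at" the investigator's discretion. Section 7.1.2, on other adverse events, says that participants "must be permanently discontinued from IMP" when a listed event occurs.

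**The concern.** One clinical event is described with three different degrees of obligation: to be considered, suggested, and required. No visible sentence says which governs. Of two careful investigators facing ALT at or above 5×ULN, or ALT and bilirubin values in the Hy's Law range, one could stop permanently and the other could continue dosing, and each could cite the protocol.

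What is at stake is participant safety and consistent conduct across sites. Permanent discontinuation also scores as non-response on the primary endpoint (SAP Section 5.3.2), but that is secondary here: the SAP plans no hypothesis testing.

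**Working it through.** The point is textual, so the check sets the provisions side by side. The only arithmetic concerns the cost of the fix.

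**1. Does the suggested heading make every action under it optional?** Not reliably. Reporting the event to the sponsor within 24 hours sits under the same heading. For potential Hy's Law, reporting is mandatory elsewhere: Section 8.3.6 treats it as an adverse event of special interest reportable within 24 hours, and the notes in Appendices 2 and 6 require it to be reported as an SAE. At least one bullet under the heading is therefore not optional in an important case.

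**2. Is the stop instruction confined to the bullets under that heading?** No. Footnote a to the Appendix 6 table repeats it: where bilirubin cannot be fractionated promptly, medication is to be discontinued if ALT is at least 3×ULN and bilirubin at least 2×ULN.

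**3. Does the rest of Appendix 6 fit an advisory reading?** Poorly. The increased-monitoring table permits continued dosing only when ALT is at least 3 and below 5×ULN, bilirubin is below 2×ULN, there are no relevant symptoms, and weekly monitoring is possible for 4 weeks. That boundary means little if continuing beyond it is also a free choice.

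**4. Does Section 7.1 settle the matter?** No. Its discretion is stated as additional to the algorithmic criteria. The Amendment 2 log explains that adverse event management should not rest on algorithms alone. Neither text says that an investigator may override a criterion that has been met.

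**5. Does the opening of Appendix 6 settle it?** No. It makes assessment compulsory, but does not say whether meeting a listed criterion decides the outcome.

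**6. What would a mandatory rule cost a participant who entered with raised ALT?** The entry limit comes from exclusion criterion 24b ("24b Alanine transaminase (ALT), aspartate aminotransferase (AST), or alkaline phosphatase (ALP) are" above 3×ULN). A sub-bullet of the same criterion still refers to 2×ULN. The gap between the entry limit and the 3×ULN stopping level is:

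- main clause: 3×ULN − 3×ULN = 0
- sub-bullet: 3×ULN − 2×ULN = 1×ULN

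Under the main clause a participant may enter at exactly 3×ULN. With ALT unchanged and no bilirubin, INR or symptom finding, that participant could meet 2 of the 6 criteria: persistence for 4 weeks, and inability to monitor weekly. This gap shows where a strict rule would bite. It does not measure the ambiguity.

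**The case against.** The strongest reply is that the criteria were meant to be advisory. Appendix 6 is titled and headed as suggested actions, its opening asks for an assessment of whether medication must stop, Section 7.1.1 speaks of considering, and Section 7.1 leaves adverse event management to the investigator. The amendment history attributes that last sentence to regulatory feedback. The word required appears only in a laboratory-table note. This gives the advisory reading real support, but it does not explain the unqualified stop instructions, the footnote that repeats them, or the bounded range for continued dosing.

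The contrast with Section 7.1.2 should not be pressed. Its mandatory list includes an infection item that also invites judgement on continuing, so mixed wording is partly this protocol's style.

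Safeguards exist. Section 8 calls for immediate safety concerns to be discussed with the sponsor, including whether treatment should continue. Appendix 6 requires an agreed monitoring plan for ALT above 3×ULN. Reporting is due within 24 hours. These provide a process for the decision; they do not state the rule.

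A reader might infer that the cross-references are circular, since the increased-monitoring table sends a participant who meets a stopping criterion back to Section 7.1.1. That cannot be shown. Section 7.1.1 includes Figure 7-1, which is missing from the copy reviewed and may contain a plain stop instruction.

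**Conclusion.** The inconsistency in the visible text is real and survives the objections in limited form. It is a minor safety clarification.

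Exposure is limited to the 12 randomised participants (SAP Section 3). SAP Section 5 says they were randomised under different protocol versions up to Amendment 5. The change logs for Amendments 1 to 6 list no edit to Section 7.1.1. Amendment 3 did revise Appendix 6 and Amendment 4 raised the entry limit from 2 to 3×ULN, so the present Appendix 6 wording and the zero gap cannot be assumed for every participant.

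Two further inferences are not supported. The documents give no liver event rate, so neither the frequency of divergent decisions nor any shift in the primary endpoint can be estimated. Nor do they establish that stopping is optional: the fault is that the text supports both readings.

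The conclusion assumes only that the extracted text is complete apart from Figure 7-1. If the figure says stop, it sits awkwardly with the sentence that introduces it; if it says consider, it conflicts with Appendix 6. Either way the wording needs aligning.

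**What to change.** State in Section 7.1.1 that a participant who meets an Appendix 6 liver chemistry stopping criterion must permanently discontinue IMP and must not be rechallenged. Keep investigator discretion for the increased-monitoring range and for stopping below the thresholds in the participant's interest. Label the Appendix 6 discontinuation actions as required, in line with Appendix 2; other follow-up tests may stay suggested. Check Figure 7-1 against the same rule.

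For a participant who entered with ALT near 3×ULN, allow a documented exception, agreed with the medical monitor, limited to the two criteria that can be met with no rise: ALT at least 3×ULN for 4 weeks or more, and ALT at least 3×ULN that cannot be monitored weekly.

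A mandatory stop fits the protocol's structure, because continued dosing is already confined to a bounded range and discretion is framed as additional to the criteria. The cost is a sentence in Section 7.1.1, a label, the short exception and a check of the figure. The downside is slightly less investigator discretion, mainly for participants who enter near the limit, which the exception addresses.
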